Protocol Title: SCH: Context-aware Freezing of Gait mitigation in real-world setting

Identification: **NCT Number**NCT04746846

Unique Protocol IdHM20020085

PI: [name]

Version Date: 6/13/2023

IRB approval date: 7/31/2023

Full Study Title: SCH: Context-aware Freezing of Gait mitigation in real-world setting

PROTOCOL DOCUMENT

4.2. Study Design:

4.2.a. Narrative Study Description

Design. This is a single site clinical trial involving 3 tasks with the purpose of development and testing feasibility of a device. In total, 32 participants with Parkinson's disease (PD) who experience freezing of gait (FoG) will complete this 3-year study. We will enroll up to 50 participants to account for screen fails and withdrawals.

Procedures. All procedures are performed exclusively for research purposes. After obtaining consent from the PD patient, a member of the research team will administer the Montreal Cognitive Assessment (MoCA) test to determine cognitive eligibility (must score at 21 or higher to be eligible). If the participant is eligible, they will be assigned a code number, then asked to complete a demographic form, a physical performance test (10-Meter Walk test) and the remaining scales in Table 1, to capture relevant physical and neuropsychological covariates.

Table 1. Physical and Neuropsychological Scales (total participant time for all the below measures is 30 minutes).

Factor	Validated Scale
Cognition	Montreal Cognitive Assessment [1]
Fatigue	Parkinson's Disease Fatigue Scale [2]
Balance Confidence	Activities-specific Balance Confidence (ABC) scale [3]
Fear of Falling	Falls Efficacy Scale-International [4]
Quality of Life	Parkinson's Disease Questionnaire-8 [5]
Freezing of Gait	New Freezing of Gait questionnaire [6]
Nonmotor Symptoms	MDS-UPDRS part 1 questionnaire [7]
Walking Speed and Step Length	10 Meter Walk Test [8]

All 32 participants will be screened with the same inclusion and exclusion criteria described in section 2.2 above. All will undergo the same consenting procedure described above. Each study participant will wear a safety belt and have trained spotters to deter falls. The specific procedures for each of the 3 tasks are as follows:

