The goals of **Task 2** are to (1) determine the optimal frequency and vibration settings to mitigate freezing of gait (FoG) and (2) explore the role of neuropsychological factors such as sleep and anxiety in FoG outcomes (see Table 1 & 2). Thus, response surface methodology is proposed. Specifically, a central composite design (CCD) [38] will be used to determine the best dose of vibration (frequency and amplitude) for each of five common triggers for FoG (Figure 1). Estimating the response surface requires only a small sample of human participants, e.g., one participant for each design point with five repeats at the center point. For the current project, a convenience sample of only 13 participants with PD who experience FoG in at least two of the scenarios, confirmed by a neurologist will be needed. The 13 participants will be asked to walk through each of five, 5-meter walking courses that will each include one of the triggering scenarios. Each of the 13 PD participants with FoG will be randomly assigned to one of 9 different *ff* and *va* settings as prescribed by the CCD. In the current case, the goal is to estimate the *ff* and *va* settings that will maximize the difference between the baseline (no vibration) and post-treatment time spent in a FoG state for each of the 5 triggering scenarios individually and in total. Measurements will be taken once at baseline and again in triplicate as they walk the paths wearing the FoG detection/vibration device.

Additional activities for Task 2 participants:

Visit #1: After the consenting process is completed, a sample of saliva will be collected (see procedure below) to measure salivary alpha amylase levels at baseline. The UG device and PDVibe3 will be placed on the participants who will then perform a 10-meter walk test on site and a baseline walk of the five triggering

scenarios. They will complete the questionnaires/scales listed in tables 1 and 2. Participants will then be instructed on how to wear the actigraph device on their dominant wrist (Actigraph GT9X Link) to collect objective sleep data for up to 14 days prior to their Visit #2. They will also be instructed on how to complete the sleep diary during the same time period during which the actigraph is collecting sleep data. Visit #1 will last approximately 90 minutes.

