Visit #3: Participants will engage in a semi-structured interview via telephone or virtually according to participant preference. The interview will ask participants to reflect on and engage in discussion related to experiences of FoG; perceptions of the association between sleep, anxiety, and FoG; illness self-concept; mobility self-efficacy; general feedback about the interview and participation in the study overall (see submitted interview protocol document). Visit #3 will last approximately 30 to 60 minutes.

Participants will be ON their PD medications during this phase of testing. The study staff, except for the PC, will be blinded to the treatment allocation. The PC will be setting the VibeForward vibration parameters (*ff* and *va*) for each participant according to a randomized list generated by the co-I and biostatistician, Dr. [name] All participants will wear safety belts and have trained spotters to deter falls. Participants will be asked to also participate in Task 3.

Task #2: Each subject is expected to spend up to 5 hours in the clinical setting, across three visits.

Updated 13JUN2023

Version 3.0

In Task 3 we will test the device at the optimal vibration setting in a “real world” setting. Due to the innovative nature of studying this device in a real-world environment, no pilot data exists from which to run a traditional power analysis. However, Van Belle proposed that a minimum of 12 observations should be used to calculate confidence intervals based on the t-statistic with $n - 1$ degrees of freedom. This rule is based on the fact that the half-width confidence interval for the mean decreases rapidly up to $n = 12$, at which point the decrease is less dramatic and the half-width curve begins to asymptotically decrease. Thus, in order to ensure the good estimates of the means and variances (pre- and post-) [39] a convenience sample of thirteen volunteers who have been diagnosed with PD by a neurologist and who exhibit FoG will be asked to participate in the testing of the device.

Participants will walk the pathway once without vibration (pre-treatment), and then three times with vibration (post treatment). They will be ON their medications. We will compare the differences in the duration and number of FoG episodes, time walking through the path, average stride length, and speed of walking. It is anticipated that “pre” versus “post” trials for each of these five variables will be compared using a paired t-test.

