All participants in Task 3 will be described in terms of demographics, disease, and psychological characteristics as in Task 2. Detailed field notes will be made of observations from study staff and comments from subjects to record the extent and type of unpredictable challenges faced by each participant. Qualitative questions will be asked after each participant finishes the walking portion of the study. If a participant from Task 2 does not participate in Task 3, they will be replaced. The replacement will then complete the baseline walking portion and scales (Table 1) from Task 2 at a separate visit prior to completing Task 3. Patients from Task 2 will be reconsented for Task 3.

When the PC contacts participants who have already completed Task 2 to participate in Task 3, the PC will ask if they want to participate in a follow-up phone call with the interviewer they spoke with earlier. If yes, the interviewer will contact the participants and will share the main overall themes that surfaced from qualitative analysis of completed interviews. Participants will be asked (via phone, zoom, or in-person) to provide their feedback on these overall themes. Their feedback will then be incorporated into final analysis and interpretation of qualitative interviews. It is anticipated that this will take from 15 – 30 minutes. Participants can decline this portion of the study.

Participants in Task 3 will walk the 5 triggering scenarios (Figure 1) in a community setting (at the Short Pump Town Center) while wearing the UG device and the PDVibe3. Prior to walking in the community setting, participants will be consented and complete the questionnaires in Table 3 in a private VCU space (at the Short Pump Pavilion clinic).

Table 3. Physical and Neuropsychological Scales (total participant time for all the below measures is 30 minutes).

Factor	Validated Scale
Cognition	Montreal Cognitive Assessment [1]
Freezing of Gait	New Freezing of Gait questionnaire [6]
Motor Symptoms	MDS-UPDRS part 3 [7]
Walking Speed and Step Length	10 Meter Walk Test [8]
Fatigue	Rating of Fatigue Scale [21]

Task #3: Each subject that completed Task 2 is expected to spend up to 5 hours in the community setting (outside setting), and clinical setting, across two visits. Each subject that did not complete Task 2 is expected to spend up to 8 hours in the VCU clinical setting and an outside community setting, across two visits.

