The CCD is specified by first defining a 2×2 factorial with four (ff , va) design points: (175, 0.55), (175, 0.75), (275, 0.55) and (275, 0.75) denoted in the plot by the solid dots (Figure 9). The design points are based on ff and va parameter settings C2 factors are capable of delivering (C2 factor datasheet) used in previous vibration research conducted by [name] (PI).

The four factorial design points are sufficient to estimate a first-order response surface that is flat (no curvature). In order to estimate a second-order response surface (or curvature in the response surface), the 2×2 factorial is augmented with axial points and multiple center points. Assuming a frequency range of 175 to 275 from the factorial portion, the axial points are defined as (154.29, 0.65), (295.71, 0.65), (225, 0.509) and (225, 0.791) denoted by the open dots emanating from the face of the cube. These axial points are chosen such that the design is rotatable, i.e., the prediction

[figure not shown]

Figure 9: The Central Composite Design

variance is constant on spheres around the center of the design. The number of center points (225, 0.65) denoted by "X") is chosen to be five to optimize estimate of the prediction variance and lack-of-fit. Thus, the full CCD with five center points will require 13 PD participants. To determine the optimal vibration frequency (*ff*) and amplitude (*va*) parameters for preventing or mitigating FoG, 13 participants will be randomly assigned to one of 9 different frequency (*ff*) and amplitude (*va*) settings as prescribed by the central composite design (CCD). Using response surface methodology, the response surface based on the baseline value minus the average of 3 post-vibration trials will be estimated yielding settings of frequency and vibration that will be the difference between the baseline and post-treatment time spent in a FoG state.

An overall optimum *ff* and *va* will be estimated using response surface methodology by fitting the following second order model:

$$y_i = \beta_0 + \beta_1 x_{1i} + \beta_2 x_{2i} + \beta_{11} x_{1i}^2 + \beta_{22} x_{2i}^2 + \beta_{12} x_{1i} x_{2i} + \varepsilon_{ij}$$

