To determine both the efficacy and generalizability of our wearable system in a real-world environment, we selected an outdoor setting where participants will all walk the same pre-determined path with a variety of real-world confounding variables (see Figure 10). Participants will walk through paths in an open-air setting with FoG triggers similar to those that were constructed in the lab setting. Participants will be asked to walk down a path approaching a chair; walk through a narrow doorway into a restroom, turn around 540 degrees, and come back out, and progress toward a time-sensitive electronic door and pass through before it closes. We anticipate other people walking around the space, intrusive noises, and various other unpredictable environmental challenges, thus presenting the participants with typical community distractions, and resulting in a more realistic evaluation of the device. There are two related research questions to answer prior to more rigorous real-world testing: 1) how to automatically and accurately detect the FoG triggering scenarios or contexts? and 2) how to adapt the vibration parameters based on the contexts? For the first question, we will use a hierarchical positioning method that combines Global Positioning System (GPS) and Bluetooth low energy (BLE) beacons. GPS determines the patient's coarse-grained location in the outdoor environment, and a series of BLE beacons that are capable of identifying the patient's fine-grained triggering scenarios in the outdoor environment. Both the GPS and BLE modules will be embedded in the

[figure not shown]

Figure 10: (A) Aerial view, of proposed real-world walking paths at an outdoor mall near the VCU clinic. (B) Example of walking path that includes approaching a visual target (chair). (C) Walking path that includes a narrow passageway (unisex restroom) where the participant can turn 540 degrees. (D) Walking path that includes a time sensitive trigger (getting through an automatic door before it closes).

participants' carried mobile device. For the second question, in each automatically detected scenario, the device will be programmed to deliver appropriate vibration doses when a FoG episode occurs.

We will evaluate the device's ability to both detect patient location within predefined locations at the outdoor setting (Figure 10), and to administer the correct dose of vibration (i.e., *ff* and *va*) when the patients are exposed to these trigger scenarios.

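### Task 3 always puts the walk without vibration first, so its paired comparison gives an uncontrolled pre/post change and not an effect of vibration

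*Protocol*

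**What the plan says.** Protocol section 4.2.a, Task 3, fixes the sequence for all thirteen participants: "Participants will walk the pathway once without vibration (pre-treatment), and then three times with vibration (post treatment". Five variables (duration and number of FoG episodes, time on the path, stride length, speed) are then handled the same way: pre and post "for each of these five variables will be compared using a paired t-test". The sample size rests on a rule of thumb for confidence-interval width, because "no pilot data exists from which to run a traditional power analysis". No alpha, effect size, power or success rule is given for Task 3.

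On purpose, the two documents differ in tone. The protocol describes the whole study as one "with the purpose of development and testing feasibility of a device". SAP section 4, which is the 2020 grant text, opens Task 3 with the aim "To determine both the efficacy and generalizability of our wearable system in a real-world environment". SAP section 5 (Real-world evaluation) presents the comparison of vibration off with vibration on as the objective test of effectiveness.

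The number of walks also differs. SAP section 4 has one walk with vibration and one without, and does not state the order. The protocol has one without and three with. Neither says how several vibration walks enter a paired t-test in Task 3. Averaging is stated only for Task 2, in SAP section 3: "the response surface based on the baseline value minus the average of 3 post-vibration trials will be estimated".

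**The concern.** Vibration status is completely tied to walk order: the OFF walk is always first and every ON walk comes later. Pairing removes differences between people. It does not remove differences between a first and a later walk in the same person.

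Such differences are plausible here. The route includes a door that must be passed before it closes and a 540-degree turn in a restroom. The Task 3 scales include a fatigue rating. The SAP expects unpredictable disturbances in the mall, which are recorded only in field notes. Practice could pass for a device benefit, and fatigue could hide one. At stake is whether a change in the walking outcomes can be reported as an effect of vibration.

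**Working it through.** **No plan figure to reproduce.** The 13 is not based on power. The cited rule behaves as described: half-width/SD = t(0.975, n−1)/√n is 0.635 at n = 12 and 0.604 at n = 13. It concerns precision, not attribution.

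**Is order controlled anywhere?** Protocol 4.2.a and SAP sections 4 and 5 contain no randomised or balanced order for Task 3, no later OFF walk, no control group and no order term. The randomised list and the staff blinding in the protocol belong to the Task 2 vibration settings.

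**Bias from the fixed order.** The ON walks have mean position (2+3+4)/3 = 3 and the OFF walk has position 1. A linear drift of τ per walk therefore adds 2τ to the difference. A step d between walk 1 and the later walks adds all of d.

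**Assumptions for the illustration** (none are in the documents): ON walks averaged per person, n = 13 as in the protocol (the SAP has 15), two-sided 5%, normal data, shifts in SD of the paired difference.

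- Paired t-test, df = 12, noncentrality = shift × √13. With no vibration effect, a shift of 0.2 gives 10.2% rejection and a shift of 0.5 gives 38.2%.
- With a true effect of 0.8, power is 75.4%. If order opposes it by 0.2 or 0.5, the net shift is 0.6 or 0.3, and power is 51.2% or 16.9%.

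**Can the planned walks repair it?** A line through walks 2–4, extrapolated to walk 1, corrects a linear drift. Let r be the variance of individual response divided by walk variance. The variance ratio to the plain contrast is (r + 10/3)/(r + 4/3), which is 2.50 at r = 0 and 1.86 at r = 1. Power for 0.8 SD falls to 39% or 49%. A step confined to walk 1 stays at full size.

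**Randomised order, same four walks and 13 people.**

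- *Single OFF walk, position randomised 4/3/3/3.* Remaining step bias: (4·d − 9·d/3)/13 = d/13. Remaining drift bias: also 1/13 of the original. Simulated rejection with no vibration effect (shifts of 0.2 and 0.5): 3.8–4.9%. Vibration walks: 13 × 3 = 39.
- *OFF-ON-ON-OFF or ON-OFF-OFF-ON, 7/6.* Without a sequence term, the remaining step bias is (7 − 6)/13 × d/2 = d/26, and the drift bias is zero. With a sequence term, any additive walk pattern cancels (df = 11) and simulated rejection is 4.9–5.1%. Variance ratio to the fixed order: (r + 1)/(r + 4/3) = 0.75 or 0.857. The sequence term multiplies this by (13/4)(1/7 + 1/6) = 1.006, giving 0.754 or 0.862. Vibration walks: 13 × 2 = 26.

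**Carry-over.** Suppose a share c of the mean effect persists into every OFF walk that follows vibration.

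- Loss of contrast: 9c/13 = 0.69c (single OFF); (7·c/2 + 6·c)/13 = 0.73c (2+2); (c/2 + c)/2 = 0.75c (2+2 with sequence term).
- At c = 0.5 and a 0.8 SD effect, power is 41%, 44–49% and 43–47% respectively. The fixed order has 75% if there is no order effect.
- Break-even for 2+2 against that 75%: c = (1 − √variance ratio)/0.731 = 0.18 (r = 0) or 0.10 (r = 1). Equating power with the sequence term (contrast 0.8(1 − 0.75c), df = 11) gives slightly less, about 0.17 or 0.08.

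**The case against.** **This is preliminary work.** The protocol calls it feasibility, and SAP section 4 places its research questions ahead of more rigorous real-world testing. The efficacy wording comes only from the 2020 grant text. An uncontrolled pre/post estimate is a defensible choice at this stage. That stands, and it limits the point to how the walking results are described. It does not remove the point, because the SAP states the efficacy aim and the protocol keeps the paired tests.

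**Participants have already practised.** In the laboratory, "Measurements will be taken once at baseline and again in triplicate as they walk the paths wearing the FoG detection/vibration device", so Task 2 completers have walked each trigger course four times. For anyone who joins only at Task 3, "The replacement will then complete the baseline walking portion and scales (Table 1) from Task 2 at a separate visit". This lowers the novelty of the tasks, but not of the community route, and it leaves participants unequally familiar with the tasks.

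**Randomising may cost more than it gains.** Carry-over is unknown, and avoiding it is a legitimate reason for putting the OFF walk first, although the documents do not give that reason. The 2+2 order loses its power advantage above roughly 10–18% carry-over. It also cuts vibration walks from 39 to 26, a one-third loss for the SAP section 4 evaluation of whether the device delivers the intended vibration settings. This stands, so a change of order should not be the lead recommendation.

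**The magnitudes are assumed.** This also stands. FoG counts and durations in 13 people may be far from normal, and the protocol does not say how the four walks fall across the two Task 3 visits.

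**Conclusion.** The point holds in a limited form. The Task 3 paired difference combines vibration with any first-versus-later effect, and the planned analysis cannot separate them. The design therefore does not support the SAP's efficacy and effectiveness statements for the walking outcomes. The 10% and 38% rejection rates, and the fall in power from 75% to 51% or 17%, show only what assumed shifts of 0.2 and 0.5 SD would do. They are not estimates of what will happen.

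A reader might infer three stronger things that the documents do not support:

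- *That the fixed order favours the device.* No order-effect size or direction is given, and fatigue would work against it.
- *That a randomised order would secure attribution to vibration.* It would deal with order, but expectation would remain, because no sham or inactive-device walk is described for Task 3.
- *That Task 3 as a whole fails.* The context-detection and survey evaluations do not rest on this contrast, and a descriptive pre/post result remains valid.

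This should be fixed, because a few sentences settle what the trial may conclude.

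**What to change.** **Minimum, in protocol and SAP:**

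1. State that the Task 3 walking outcomes give an uncontrolled pre/post change that is not attributable to vibration, and bring the SAP's efficacy and effectiveness wording into line.
2. Report the mean of each outcome for each of the four walks, so that any drift over walks 2–4 can be seen.
3. State that the three vibration walks are averaged per participant before the paired t-test.
4. Reconcile the number of walks: SAP section 4 against protocol 4.2.a, Task 3.

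This costs only wording and one table. It gives up the efficacy claim.

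**If the team judges carry-over into later OFF walks to be small,** randomise order within the same four walks and 13 participants, in one of two ways:

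- Randomise the position of the single OFF walk (4/3/3/3) and compare it with that participant's mean of the ON walks. All 39 vibration walks are kept. At a 0.5 SD order shift the variance rises by 9–10% for a first-walk step or 15–16% for a linear drift.
- Randomise to OFF-ON-ON-OFF or ON-OFF-OFF-ON (7/6) and analyse each participant's OFF mean minus ON mean with a sequence term. This costs one degree of freedom and leaves 26 vibration walks.

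Either needs a short randomisation list and no extra visits. In both, carry-over shrinks the contrast by about 0.7 of the share carried over, and expectation effects stay and should be named as a limitation.

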Protocol Title: SCH: Context-aware Freezing of Gait mitigation in real-world setting

Identification: **NCT Number**NCT04746846

Unique Protocol IdHM20020085

PI: [name]

This is the original grant

IRB approval date: 9/24/2020

classification. Normally, the window length is set to cover several walking steps, which leads to delay of vibration mitigation. During this delay period, the patients have an increased risk of falls.

2. How to construct the FoG detection model using unbalanced data samples? As FoG typically happens intermittently, the collected positive class samples (i.e., FoG gaits) are fewer than the collected negative class (i.e., normal gaits) samples. However, to adequately train deep learning algorithm-based FoG detection models, several hours of FoG episode data are required for each patient and each application scenario. The shortage of FoG data may cause the detection results to be biased toward the negative class.
3. How to differentiate between FoG and an abrupt stop? We need the ability to detect FoG pattern versus normal cessation of walking, thereby providing a practical solution in a real-world setting.

In the following subsections, we present our solutions to answer each of the above research questions, and how we plan to validate our process.

